#### **13.4 National Institutes of Health (NIH) Eye Score**

NIH Eye Score will be collected at Visits 1, 5, and 7.

The score ranges from 0 to 3 as follows:

- Score 0: No symptoms
- Score 1: Mild dry eye symptoms not affecting Activities of Daily Life (ADL) (requirement of lubricant eye drops  $\leq 3$  x per day)
- Score 2: Moderate dry eye symptoms partially affecting ADL (requiring lubricant eye drops  $> 3$  x per day or punctal plugs), WITHOUT new vision impairment due to keratoconjunctivitis sicca (KCS)
- Score 3: Severe dry eye symptoms significantly affecting ADL (special eyewear to relieve pain) OR unable to work because of ocular symptoms OR loss of vision due to KCS

Continuous descriptive statistics will be used to summarize the eye scores by visit and treatment group. Change from baseline will also be summarized.

Wilcoxon Rank Sum tests will be used to compare Pro-ocular to placebo for the visit score and for the change from baseline. Wilcoxon Rank Sum Tests will be truncated to visit 5 and any data after visit 5 will be summarized with counts and percentages.

During the Study Treatment Phase, the changes from baseline will be relative to the Study Treatment Phase baseline. During the Placebo Cross-over Phase, the changes from baseline will be relative to the Placebo Cross-over Phase baseline.

Analyses will be performed on the ITT population using observed data only.

All NIH Eye Scores will be presented in a subject listing.

#### **13.5 Chronic ocular GvHD Signs**

The evaluations included as part of the Chronic ocular GvHD Signs are described below.

### 13.5.1 TearScan Examination

TearScan examinations will be conducted at Visits 2 – 7 (both pre-dose and post-dose at Visit 2). The TearScan will examine the tear film and lid margin as well as meibum expression.

Tear film will be assessed by eye using a VAS with anchors No Tear Film 0, Tear Film Visible 1, Reliable Tear Film 2, and Copious Tear Film 3.

Red eyelids will be assessed by Yes or No.

Meibomian gland expression will be assessed by eye using a VAS with anchors None, Few, and Many.

For each VAS, the Investigator will mark a vertical slash on the VAS to indicate the level of severity.

The result (in mm) will be measured from the left endpoint to the slash marked by the Investigator on the line.

A score is derived by converting the measure length to a maximum score of 3 with one decimal place as follows:

$$\text{Score} = \text{Measured Result (mm)} * 3 / \text{CRF Scale Length (mm)}$$

Continuous descriptive statistics will be used to summarize the results by eye type, visit and treatment group. Change from baseline will also be summarized.

Two sample t-tests will be used to compare Pro-ocular to placebo for the visit score and for the change from baseline.

During the Study Treatment Phase, the changes from baseline will be relative to the Study Treatment Phase baseline. During the Placebo Cross-over Phase, the changes from baseline will be relative to the Placebo Cross-over Phase baseline.

The number and percentage of subjects with red eye will be presented by eye type, treatment, and visit.

Analyses will be performed on the ITT population using observed data only.

All TearScan results will be presented in a subject listing.

### 13.5.2 Visual Acuity

Visual acuity in each eye will be measured at Visits 1 and 5 using a Snellen chart, then pinhole test, both distance visual acuity and near visual acuity. Visual acuity is based on the current corrected vision, with correction if wearing glasses, or without correction if not wearing glasses. Snellen scores will be transformed into logMAR scores as follows:

$$\text{Snellen Base score} - 0.02 * (\text{number of correct letters from next smaller line}) \text{ or}$$

$$\text{Snellen Base score} + 0.02 * (\text{number of correct letters from previous larger line})$$

where the Snellen Base score is the logMAR equivalent score defined below in Table 3.

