## **8.4 Data Analysis Conventions**

The Primary analysis will be performed by Statistics & Data Corporation (SDC) after the Study Treatment Phase is completed and the database has been locked and released for unmasking. An additional analysis will be completed once the Cross-over Phase is completed and the database for that portion is locked. Statistical programming and analyses will be performed using SAS® version 9.4 or higher. Output will be provided in rich text format (RTF) for tables, Excel format for tables and listings, and portable document format (PDF) for figures using landscape orientation for any PDF or RTF. All study data will be listed by subject, treatment, and visit (as applicable) based on all randomized subjects unless otherwise specified.

Summaries for continuous and ordinal variables will include the number of observations (n), arithmetic mean, standard deviation (SD), median, minimum, and maximum. Minima and maxima will be reported with the same precision as the raw values; means and medians will be presented to one additional decimal place than reported in the raw values. Standard deviations will be presented to two additional decimal places than reported in the raw values. Summaries for discrete variables will include counts and percentages. All percentages will be rounded to one decimal place (ie, XX.X%). Differences between active treatment group and placebo will be calculated as active minus placebo and change from baseline will be calculated as follow-up visit minus baseline.

All statistical tests will be two-sided with a significance level of 0.05 ( $\alpha = 0.05$ ) unless otherwise specified. Confidence intervals (CI) for differences between treatment groups will be two-sided at 95% confidence intervals. All p-values will be rounded to 4 decimal places; p-values less than 0.0001 will be presented as "<0.0001"; p-values greater than 0.9999 will be presented as ">0.9999."

Unless otherwise specified, summaries will be presented by treatment group and, where appropriate, visit. Listings will be sorted by treatment group, subject number, visit/time point, and parameter as applicable.

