**Table 3. Snellen Base Scores and LogMAR Conversions**

Snellen Base Score	LogMAR Score
20/200	1.00
20/160	0.90
20/125	0.80
20/100	0.70
20/80	0.60
20/63	0.50
20/50	0.40
20/40	0.30
20/32	0.20
20/25	0.10
20/20	0.00
20/16	-0.10
20/12.5	-0.20
20/10	-0.30

The observed and change from baseline visual acuity will be summarized for each eye (worse eye and fellow eye) using continuous descriptive statistics by visit for each treatment group and for all actively treated subjects. A subject listing of visual acuity will also be produced.

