## 14.2 Visual Acuity

Visual acuity is discussed in section 13.5.2 for the efficacy analysis. For safety, continuous descriptive statistics will be used to summarize visual acuity by eye and treatment group. Change from baseline will also be summarized. The Safety table will be produced with an additional categorical summary of subjects with logMAR change from baseline  $\geq 0.20$  logMAR and both eyes, Right Eye (OD) and Left Eye (OS) will be the unit of analysis.

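### As written, the second logMAR formula gives a worse score the more letters are read, so the safety count of changes of at least 0.20 logMAR can be wrong

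*SAP*

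**What the plan says.** SAP Section 13.5.2 offers two formulas joined by 'or'. The first starts from a base score and subtracts 0.02 times the "number of correct letters from next smaller line". The second starts from a base score and adds 0.02 times the "number of correct letters from previous larger line". The base comes from Table 3 of that section ("where the Snellen Base score is the logMAR equivalent score defined below in Table 3"), which runs from 1.00 at 20/200 to -0.30 at 20/10 in steps of 0.10. The section does not say which line is the base, when each formula applies, or how many letters a line has.

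The resulting scores are used in two places. As an additional efficacy variable, "The observed and change from baseline visual acuity will be summarized for each eye" by descriptive statistics. For safety, Section 14.2 adds an "additional categorical summary of subjects with logMAR change from baseline" of at least 0.20, for right and left eyes. Under Section 8.4, "change from baseline will be calculated as follow-up visit minus baseline", so a positive logMAR change is a loss of acuity.

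**The concern.** On a scale where higher is worse, letters read correctly must lower the score or leave it unchanged. The first formula respects this and the second reverses it. The two can therefore give different scores for the same performance on the chart.

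At stake are the logMAR means and changes (Tables 14.2.8 and 14.3.5.1) for eyes recorded as a line minus some letters, and the safety count at 0.20 logMAR. Acuity is taken only at Visits 1 and 5 under the SAP, so each eye has one follow-up value and no later one to expose a scoring error. The arms are small. One misclassified subject moves an arm's percentage by 1/22 = 4.5 points (Pro-ocular) or 1/11 = 9.1 points (placebo).

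**Working it through.** **Inputs**
- Table 3 base scores: 20/80 = 0.60, 20/63 = 0.50, 20/50 = 0.40, 20/40 = 0.30. All 14 entries reproduce as log10(denominator/20) rounded to one decimal; for 20/40, log10(2) = 0.301, giving 0.30. The table itself is sound.
- Letter value: 0.02 (Section 13.5.2).
- Letters per line: 0.10 / 0.02 = 5. This is inferred; the SAP does not state it.
- Change: follow-up minus baseline (Section 8.4). Cut-off: 0.20 (Section 14.2).

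**Step 1. One performance, scored both ways.** The eye reads all of 20/50 and four of five letters on 20/40.
- First formula, base 20/50: 0.40 - 0.02 × 4 = 0.32.
- Second formula, base 20/40, counting all five letters of the larger line (interpretation 1): 0.30 + 0.02 × 5 = 0.40.
- Second formula, base 20/40, counting the correct letters on the partly read line (interpretation 2): 0.30 + 0.02 × 4 = 0.38.
- Second formula with the one missed letter in place of correct letters: 0.30 + 0.02 × 1 = 0.32, which agrees with the first formula.

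**Step 2. Size of the error for 20/40 minus k letters.** The right score is 0.30 + 0.02k, which equals the first formula's 0.40 - 0.02(5 - k). The error is 0.02(5 - k) under interpretation 1 and 0.02(5 - 2k) under interpretation 2.

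| k missed | Right score | Interpretation 1 (error) | Interpretation 2 (error) |
|---|---|---|---|
| 1 | 0.32 | 0.40 (+0.08) | 0.38 (+0.06) |
| 2 | 0.34 | 0.40 (+0.06) | 0.36 (+0.02) |
| 3 | 0.36 | 0.40 (+0.04) | 0.34 (-0.02) |
| 4 | 0.38 | 0.40 (+0.02) | 0.32 (-0.06) |

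Interpretation 1 gives 0.40 however many letters are missed. Interpretation 2 reverses the order: the eye missing one letter and the eye missing four exchange scores.

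**Step 3. A third, more literal interpretation.** Base 20/40, with c of five letters correct on 20/50 and 20/63 fully read. For c = 1 to 5 the first formula from 20/63 gives 0.50 - 0.02c = 0.48, 0.46, 0.44, 0.42, 0.40. The second gives 0.30 + 0.02c = 0.32, 0.34, 0.36, 0.38, 0.40. The errors are -0.16, -0.12, -0.08, -0.04 and 0. The formulas agree only when the whole larger line is read.

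**Step 4. Effect on the 0.20 category.**
- Missed loss: 20/40 minus 1 to 20/80 plus 3. Follow-up is 0.60 - 0.06 = 0.54. True change 0.54 - 0.32 = 0.22. Scored 0.54 - 0.40 = 0.14 (interpretation 1) or 0.54 - 0.38 = 0.16 (interpretation 2). Not counted.
- False loss: 20/40 plus 2 to 20/50 minus 1. Baseline is 0.30 - 0.04 = 0.26. True change 0.42 - 0.26 = 0.16. Scored 0.50 - 0.26 = 0.24 (interpretation 1) or 0.48 - 0.26 = 0.22 (interpretation 2). Counted.

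**Step 5. Which true changes are exposed.** All pairs of baseline and Visit 5 scores on the Table 3 lines were enumerated under interpretation 2.
- With at most two extra or two missed letters (an assumption), the error in change runs from -0.06 to +0.06. True changes of 0.14 to 0.18 can be counted, and true changes of 0.22 to 0.24 missed.
- With up to four letters, the error reaches ±0.12. True changes of 0.14 to 0.18 can be counted, and 0.20 to 0.26 missed.

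**The case against.** The strongest reply is that this is a slip of one word, 'correct' for 'missed', which a competent programmer would put right. It is also said that the first formula alone can score every partly read line except letters missed on 20/200, so the second need never be used. Both points may be true. The documents do not show the program, and no actual miscount is demonstrated. But the SAP is the specification: a programmer following it literally, or a second one validating against it, would reproduce the error. Nothing else in the documents corrects it. The protocol gives no conversion, and SAP Section 16 does not mention acuity.

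Second, the protocol's visual acuity form has one blank per eye and no field for letters gained or missed. If only whole lines were recorded, neither letter term would matter. That stands as a limit on how often the problem arises, although the SAP formulas presuppose letter counts.

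Third, the consequence is small. Acuity is an additional efficacy variable, it is summarised without a test, and the category flips only for an affected eye whose true change is near 0.20. The examples above were chosen there. A subject listing of acuity is planned and might let a discrepancy be traced if it shows the recorded Snellen values, which the SAP does not specify. This stands, and it limits the weight of the point without removing it.

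Fourth, replacing 'correct' by 'missed' reconciles the formulas only with five letters per line. With four, 20/50 plus 3 gives 0.40 - 0.06 = 0.34, but 20/40 minus 1 gives 0.32. With six, 20/50 plus 5 gives 0.30, but 20/40 minus 1 gives 0.32. This stands, and the fix has to state the letter count.

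**Conclusion.** The second formula is wrong as written. It conflicts with the first under all three interpretations tried, except in the trivial case where the larger line is fully read and simply returns its own score. With five letters per line, the error in a single score is +0.02 to +0.08, -0.06 to +0.06, or -0.16 to 0, depending on the interpretation. The count of changes of at least 0.20 logMAR can then be wrong in both directions.

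The conclusion rests on five letters per line, which is inferred, and on the rule being programmed literally and applied to eyes with letter-level records. How often that would happen cannot be derived from the documents. The two hypotheses on the GLIA and SANDE questionnaires are unaffected. The correction should be made because the rule feeds a listed safety variable.

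**What to change.** Keep the first formula. Change the second to: Snellen Base score + 0.02 × (number of letters missed on the base line). Then add:
- the base line is the Snellen line as recorded;
- the first formula applies when extra letters are read on the next smaller line (line plus n), the second when letters are missed on the base line (line minus n);
- each line is scored as five letters, and if the chart used has a different number per line, the 0.02 per letter must be revisited.

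Test the derivation program on one case scored both ways: 20/50 plus 4 and 20/40 minus 1 must both give 0.32.

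The cost is one corrected line, these short definitions and a program check. No new data are needed and there is no downside.

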**Table 3. Snellen Base Scores and LogMAR Conversions**

Snellen Base Score	LogMAR Score
20/200	1.00
20/160	0.90
20/125	0.80
20/100	0.70
20/80	0.60
20/63	0.50
20/50	0.40
20/40	0.30
20/32	0.20
20/25	0.10
20/20	0.00
20/16	-0.10
20/12.5	-0.20
20/10	-0.30

The observed and change from baseline visual acuity will be summarized for each eye (worse eye and fellow eye) using continuous descriptive statistics by visit for each treatment group and for all actively treated subjects. A subject listing of visual acuity will also be produced.

### 13.5.3 Slit Lamp without Staining

Slit lamp biomicroscopy examinations without staining will be performed at Visit 1 and Visits 3 – 7. The exam will assess the following components, by eye:

- Lids (erythema, edema, lid margin ulceration, lid margin notches, entropion/ ectropion, trichiasis/madarosis, floppy eyelids, hordeolum (stye))
- Conjunctiva (hyperemia, cicatricial changes, pseudomembranes, chalasis)
- Cornea (edema, corneal ulcers, filamentous keratitis, corneal thinning, corneal neovascularization, scars, conjunctival epithelium invasion, limbal thickening)
- Anterior Chamber (cells, flare)
- Lens (status, opacity)

A VAS ranging from None to Most will be used to score each component except for Lens.

The Investigator will mark a vertical slash on the VAS to indicate the level of severity.

The result (in mm), will be measured from left endpoint to the slash marked by the Investigator on the line.

For each component, a score is derived by converting the measure length to a maximum score of 10 with one decimal place as follows:

$$\text{Score} = \text{Measured Result (mm)} * 10 / \text{CRF Scale Length (mm)}$$

The Investigator will classify any abnormal results as Abnormal Clinically Significant (CS), or Abnormal Not Clinically Significant (NCS), including any other pathologies noted by the Investigator.

The Lens status will be classified as Phakic, Pseudophakic or Aphakic. For Phakic lens, the Lens Opacity will be scored as 0, +1, +2, or +3.

All continuous slit-lamp measures will be analysed the same as Glia Ocular Surface Disease Symptoms Questionnaire and the modified SANDE Questionnaire with the following exceptions. Only the ITT populations using observed cases will be performed and no adjustments for multiplicity will be applied.

The abnormal findings will be summarized using counts and percentages for each treatment group at each visit for each eye. Percentages will be based on the number of subjects in each treatment group with responses. Shift tables will also be provided comparing each follow-up visit to baseline.

During the Study Treatment Phase, the changes (or shifts) from baseline will be relative to the Study Treatment Phase baseline. During the Placebo Cross-over Phase, the changes (or shifts) from baseline will be relative to the Placebo Cross-over Phase baseline.

Analyses will be performed on the ITT population using observed data only.

All slit lamp results will be presented in a subject listing.

#### **13.5.4 Corneal and Conjunctival Fluorescein Staining**

Corneal and conjunctival examinations with fluorescein staining will be performed at Visit 1 and Visits 3 – 7.

The exam will assess the following components, by eye:

- Cornea (inferior, superior, central)
- Conjunctiva (inferior, superior, temporal, nasal)

A VAS ranging from None to Most will be used to score each component.

The Investigator will mark a vertical slash on the VAS to indicate the level of severity.

The result (in mm) will be measured from left endpoint to the slash marked by the Investigator on the line.

For each component, a score is derived by converting the measure length to a maximum score of 10 with one decimal place as follows:

$$\text{Score} = \text{Measured Result (mm)} * 10 / \text{CRF Scale Length (mm)}$$

The Investigator will classify any abnormal results as Normal, Abnormal CS, or Abnormal NCS, including any other pathologies noted by the Investigator.

The corneal sum score will be the sum of scores from the inferior, superior, and central regions. The conjunctival sum score will be the sum of scores from the inferior, superior, temporal, and nasal regions.

Continuous descriptive statistics will be used to summarize each score by visit and treatment group. Change from baseline will also be summarized.

Two sample t-tests will be used to compare Pro-ocular to placebo for the visit score and for the change from baseline.

The abnormal findings will be summarized using counts and percentages for each treatment group at each visit for each eye. Percentages will be based on the number of subjects in each treatment group with responses. Shift tables will also be provided comparing each follow-up visit to baseline.

During the Study Treatment Phase, the changes (or shifts) from baseline will be relative to the Study Treatment Phase baseline. During the Placebo Cross-over Phase, the changes (or shifts) from baseline will be relative to the Placebo Cross-over Phase baseline.

Analyses will be performed on the ITT population using observed data only.

All fluorescein staining results will be presented in a subject listing.

#### **13.5.5 Facial Presentation and Blinks per Minute**

The blinks per minute will be measured with Video Capture Manual Analysis (VCMA) at Visits 2 – 7 (both pre-dose and post-dose at Visit 2). A 1-minute video will be captured for each subject while subjects are under normal conditions. The Investigator will count the number of times the subject has complete or incomplete blinks within a 1 minute  $\pm$  5 second interval.

The facial presentation score at the start of the session will also be captured (0 = eyes closed, 1 = eyes partially open, 2 = eyes fully open).

Continuous descriptive statistics will be used to summarize the number of blinks by visit and treatment group. Change from baseline will also be summarized.

Two sample t-tests will be used to compare Pro-ocular to placebo for the visit score and for the change from baseline.

Analyses will be performed on the ITT population using observed data only.

All facial presentation and blinks per minute results will be presented in a subject listing.

### **14. Safety Analyses**

All safety analyses will be conducted using the Safety population using observed data only. All analyses will be conducted separately for the Study Treatment Phase and the Placebo Cross-over Phase.

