### 3. Study Design and Procedures

#### 3.1 General Study Design

This is a Phase 2 randomized, single-center, parallel, double-masked, placebo-controlled study assessing the safety and efficacy and the of Pro-ocular™ 1% topical gel administered twice daily for 70 days in ameliorating symptoms and signs of chronic ocular GvHD.

Thirty-three subjects will be enrolled and randomly assigned in a 2:1 ratio to one of two treatments arms:

- Pro-ocular™ 1% topical gel (22 subjects)
- Placebo (11 subjects)

After a Screening visit to assess eligibility, subjects will enter a double-masked 70-day Study Treatment Phase (Visit 2 – Visit 5). Upon completion of the double-masked phase, subjects who were originally randomized to Placebo will cross-over into an open-label Placebo Cross-over Phase and will receive Pro-ocular 1% topical gel for twice-daily administration over 6 weeks (Visit 5 – Visit 7).

Analyses will be conducted separately for the Study Treatment Phase and the Placebo Cross-over Phase. The analysis of the Study Treatment Phase is the Primary analysis, and the analysis of the Placebo Cross-over Phase is secondary.

Study visits will be referred to in all tables and listings as the expected study day corresponding to the visit to enable reviewers to understand the assessment timing without referring to the protocol visit schedule. Listings, tables and figures will include visits and study days in the following format: Visit 1 (Day -14), Visit 2 (Day 1), Pre-Dose, Visit 2 (Day 1), Post-Dose, Visit 3 (Day 14), Visit 4 (Day 42), Visit 5 (Day 70), Visit 6 (Week 3) and Visit 7 (Week 6).

**Table 1** shows the scheduled study visits, their planned study day, and the acceptable visit window for each study visit.

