#### 5. Sample Size and Power Considerations

This study will randomize 33 subjects (22 to Pro-ocular™ 1% topical gel, and 11 to Placebo).

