#### **14.1 Adverse Events**

All adverse events will be collected, whether potentially related or unrelated to study drug use. Study drug includes the investigational drug under evaluation and placebo given during any stage of the study.

Treatment-emergent adverse events (TEAE) are defined as any event that occurs on or after the day that randomized study treatment is initiated. Adverse events recorded in the CRF which began prior to treatment will not be included in the summary tables but will be included in the AE data listings.

The severity of each AE will be evaluated as Mild, Moderate or Severe.

The relationship of each AE to the study drug will be determined by the Investigator as None, Possibly Related, or Probably Related.

Action taken with study drug will be classified as None, Permanently Discontinued, Temporarily Discontinued, or Other.

An overall summary will be presented that includes the number of events and the number and percentage of subjects who experienced at least one TEAE, by treatment group. This summary will also include breakdowns of TEAEs further categorized as ocular or non-ocular, treatment-related TEAEs, serious AEs (SAE), and TEAEs leading to early treatment discontinuation.

Additional summaries of TEAEs will be provided showing the number and percentage of subjects who experienced at least one TEAE by treatment group and over all subjects. Non-ocular TEAEs will be summarized using discrete summary statistics and presented by treatment group at the subject and event level by SOC and PT. Ocular TEAEs will be similarly summarized at the subject level. If a subject reports the same PT multiple times within the same SOC, that PT will only be reported once within that SOC. As with the PT, if a subject reports multiple conditions within the same SOC, that SOC will only be reported once. In the summary, SOCs will be listed in ascending alphabetical order; PTs will be listed in order of descending frequency for all subjects within each SOC.

Separate summaries will be provided for the following categories of AEs:

- Overall AE Summary
- TEAEs
- TEAEs by Relationship to Study Medication
- Treatment Emergent SAEs

All AEs will be presented in a subject listing.

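### No planned adverse event summary combines all Pro-ocular exposure across the masked and cross-over phases, and no exposure-adjusted rate is planned

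*SAP*

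**What the plan says.** The design gives Pro-ocular to two sets of people. SAP Section 5 says: "This study will randomize 33 subjects (22 to Pro-ocular™ 1% topical gel, and 11 to Placebo". Under Section 3.1 both arms are treated for 70 days in the masked phase, after which placebo subjects receive "Pro-ocular 1% topical gel for twice-daily administration over 6 weeks", open label.

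For safety, SAP Section 14 sets one rule: "All analyses will be conducted separately for the Study Treatment Phase and the Placebo Cross-over Phase". Within that rule, Section 14.1 plans the "number of events and the number and percentage of subjects who experienced at least one TEAE, by treatment group". It adds summaries by treatment group and across all subjects. Non-ocular events are shown by class and term at subject and event level, ocular events at subject level. The four adverse event tables listed in Section 19 (14.3.1.1 to 14.3.1.4) name no combined on-drug group and no rate.

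Two other places bear on the point:
- Section 12 calculates exposure in days per subject and phase, and Table 14.1.5 reports it. No adverse event summary uses it as a denominator.
- Section 13.5.2 is the only place that names a combined active group. It summarises visual acuity "by visit for each treatment group and for all actively treated subjects". Acuity is measured only at Visits 1 and 5, so that group brings in no cross-over data.

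A treatment-emergent event is "any event that occurs on or after the day that randomized study treatment is initiated".

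**The concern.** Safety is part of the primary objective (SAP Section 2), and the trial is small. Of the up to 33 people who use Pro-ocular by Visit 7, one third do so only in the cross-over phase. If each phase is summarised alone, a drug-related event seen once in each appears as a single case in two separate tables. The tightest statement about events not seen then rests on 22 subjects, although more were exposed.

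The cross-over results also cannot be read directly beside the masked results. They come from 6 weeks rather than 10, so at the same weekly rate both the event total and the percentage of subjects affected will be lower. Raw event totals differ across all three groups for reasons of size and duration alone.

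**Working it through.** **Inputs.** 22 and 11 randomised subjects (SAP Section 5). Masked phase 70 days (Section 3.1), and 70/7 = 10 weeks. Cross-over from Day 70 to Day 112 (SAP Table 1), and 42/7 = 6 weeks. The documents give no event risk, so the risks and rates below are assumptions.

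**The plan's own figure.** At 2:1, 33 × 2/3 = 22 and 33 × 1/3 = 11, which sum to 33. The split reproduces. The documents state no safety precision figure to check.

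**Planned exposure**
- Pro-ocular, masked: 22 × 10 = 220 subject-weeks
- Placebo, masked: 11 × 10 = 110
- Pro-ocular, cross-over: 11 × 6 = 66
- Any Pro-ocular: 220 + 66 = 286, and 286/220 = 1.30, so 30% more on-drug time

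**What raw totals and percentages would show with no drug effect.** Take an assumed 0.05 events per subject-week in every group. Expected events are 0.05 × 220 = 11.0, 0.05 × 110 = 5.5 and 0.05 × 66 = 3.3. The proportion of subjects with at least one event is 1 − exp(−0.05 × weeks): 39.3%, 39.3% and 25.9%. Totals therefore differ across all three groups. Percentages agree for the two randomised arms and fall only in the 6-week group. At assumed rates of 0.02 and 0.10 the percentages are 18.1%, 18.1%, 11.3% and 63.2%, 63.2%, 45.1%, the same pattern.

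**Upper bound when no event is seen (one-sided 95%)**
- Per subject, 1 − 0.05^(1/n): n = 11 gives 23.8%, n = 22 gives 12.7%, n = 33 gives 8.7%. The last figure treats 6 weeks as carrying the same risk as 10.
- Per 100 subject-weeks at a constant rate, −ln(0.05)/T × 100: T = 220 gives 1.36 and T = 286 gives 1.05.

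**Chance of seeing at least one case**
- Equal risk per subject whatever the duration: 1 − (1 − p)^n with n = 22 or 33.
- Constant hazard with 10-week risk p: h = −ln(1 − p)/10, then 1 − exp(−h × T) with T = 220 or 286.

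| Assumed 10-week risk | Masked active arm only | Combined, constant hazard | Combined, equal per-subject risk |
|---|---|---|---|
| 2% | 36% | 44% | 49% |
| 5% | 68% | 77% | 82% |
| 10% | 90% | 95% | 97% |

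**Ceiling.** SAP Section 16 mentions one early discontinuation, arm not stated. If that was a placebo subject who did not cross over, 32 are exposed and the per-subject bound is 1 − 0.05^(1/32) = 8.9%.

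**The case against.** The strongest reply is that keeping a masked, controlled phase apart from a shorter, open-label phase without a control is a deliberate and conservative choice. Section 3.1 names one primary and the other secondary. Extra analyses may be added in the study report (SAP Sections 1 and 16). All adverse events go into one listing (16.2.6) and exposure days are tabulated, so in a trial of this size a reader could derive a combined count and a crude rate. All of that stands, and it is why the phase tables should remain. It does not amount to a planned summary, and a reader should not have to build one from listings.

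Three stronger readings are tempting, and the documents do not support them:
- *Safety is reported only as raw counts, so the arms cannot be compared.* Section 14.1 also gives the number and percentage of subjects affected. With 70 planned days in both arms, those percentages compare 22 with 11 fairly, and they deal with the doubling of counts that 2:1 allocation produces.
- *The all-subjects column always mixes drug with placebo.* It does so only in the masked phase. Everyone in the cross-over phase takes Pro-ocular.
- *Events that began on placebo will be counted in the cross-over tables.* The treatment-emergent definition is tied to the start of randomised treatment and is not reset for the cross-over. But the phase split in Section 14 and the reset baseline in Section 8.3 largely cover this. What remains is a gap in wording that one sentence closes.

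**Conclusion.** The point holds as a cheap improvement to the safety reporting, not as a flaw in the randomised comparison. The SAP plans no adverse event summary of all Pro-ocular use through Visit 7 and no exposure-adjusted rate. The denominator problem is limited to raw event totals and to the 6-week cross-over column.

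The gain from combining is moderate and depends on how risk builds over time. The per-subject bound falls by about a third, from 12.7% to 8.7%, only if 6 weeks carries the full 10-week risk. At a constant rate, the bound per 100 subject-weeks falls by 1 − 220/286 = 23%. For an assumed 5% risk, the chance of seeing a case should be quoted as a range of 77% to 82%, against 68%; the upper end alone would be the favourable case. All figures use planned numbers and durations and assume that every placebo subject crosses over and completes 6 weeks.

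**What to change.** Keep the phase-specific tables. Add to SAP Section 14.1 and the Section 19 list one descriptive table, produced at the final lock:
- **Columns:** Placebo; Pro-ocular (masked phase); Pro-ocular (cross-over); Any Pro-ocular through Visit 7. The last label needs its cut-off because the protocol's open-label phase runs on to 27 months, beyond the SAP's coverage.
- **Rows:** number and percentage of subjects with a treatment-emergent event, and events per 100 subject-weeks, using the Section 12 durations.
- **Assignment rule:** each event belongs to the treatment being taken at onset, and the cross-over column counts only events that start on or after the first Pro-ocular dose.

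The cost is a few sentences and one table. Onset dates are already on the adverse event log, and exposure durations are already derived. The drawback is that the cross-over data are open-label, shorter and without a concurrent control. The combined column should be labelled descriptive and should not replace the masked comparison.
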